Radiographic assessment (CT or MRI) for evaluation of disease response will be conducted every 6 weeks (± 5 days) for the first 8 assessments (ie, through week 48) and every 8 weeks (± 5 days) thereafter from C1D1, independent of dose delays and/or dose interruptions, and/or at any time when progression of disease is suspected. For subjects who discontinue study drug/placebo for reasons other than disease progression or start of another anticancer agent, an assessment will be conducted at the EOT Visit. Upon request by the Investigator, the subjects and site staff will be unblinded to treatment assignment after documented disease progression (as assessed by the Investigator) in consultation with the Sponsor Medical Monitor, and subjects randomized to the placebo arm who continue to meet eligibility criteria determined in the EOT visit will be given the opportunity to cross over to the active treatment arm and receive AG-120. For those subjects who cross over, placebo will not be counted as a prior line of therapy for the purpose of eligibility. If subjects cross over, they will start again with study procedures as at C1D1. These subjects will continue to be evaluated for tumor response by the Investigator. If the treatment assignment is determined to be AG-120 upon radiographic disease progression, the Investigator may consider continuing treatment with AG-120, provided the subject is clinically benefitting and there is no contraindication to continuing treatment beyond progression (see Section 9.8 for parameters for treating beyond progression). Target and non-target lesion selection and objective tumor response assessments per Response Evaluation Criteria in Solid Tumors (RECIST) v1.1 will be performed by the institutional radiologist(s). An independent central review of response will be conducted by an Independent Radiology Center (IRC) per RECIST v1.1. All scans will be sent to the IRC as detailed in the site-specific Imaging Core Manual (see Section 10.7.2).

HRQOL assessments will be conducted pre-dose on C1D1 and on Day 1 of every cycle thereafter until EOT. After EOT visit, the HRQOL will be conducted every 12 weeks until the start of new anticancer therapy. One additional HRQOL assessment will also be conducted at the safety follow-up visit. Health economic outcomes assessments will occur pre-dose on C1D1, C3D1, and at the EOT Visit. Compliance assessments will occur at C1D15, Day 1 of every cycle

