¹⁸ Tumor assessments will include all known or suspected disease sites. CT imaging of the chest, abdomen, and pelvis (Torso) with triphasic IV contrast should be performed at baseline and on study. For subjects with allergy to IV iodine contrast, CT chest without IV contrast and MRI abdomen with IV contrast should be performed at baseline and on study. Brain scans with CT or MRI should be performed at baseline in subjects with known treated brain metastases and on study at the same imaging time points as Torso imaging. Bone scans will be performed at baseline if disease is suspected and on study at the same imaging time points as Torso imaging. Radiographic assessment (CT or MRI) for evaluation of disease response to be conducted at Screening (Day -21), every 6 weeks (± 5 days) for the first 8 assessments (ie, through week 48), and then every 8 weeks (± 5 days) thereafter independent of dose delays and/or dose interruptions, and/or at any time when progression of disease is suspected. For subjects randomized to placebo who receive palliative radiotherapy after unblinding and during the cross over period, a repeat CT or MRI will be performed at the end of the 2-week washout period after radiotherapy to document the area that was irradiated and to serve as the new baseline against which all subsequent RECIST v1.1 assessments will be performed, for the purpose of documenting PFS2 during the unblinded open-label cross over period (see Section 12.12.1). For subjects permitted to continue on open-label AG-120 beyond documented radiographic progression, a new baseline imaging assessment will not be required and the imaging assessments will continue on the current schedule. Any ancillary findings on the radiographic assessments will be communicated to the appropriate physician for notification to the subject. All scans obtained will be sent to the IRC, as detailed in the site-specific Imaging Core Manual (see Section 10.7.2).

¹⁹ Extent of disease will be assessed based on RECIST v1.1.

²⁰ Response to treatment is to be assessed at this visit if the subject discontinues treatment for reasons other than disease progression or start of another anticancer therapy.

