²¹ If a subject goes off treatment for reasons other than disease progression, response assessments will be conducted at the EOT Visit and every 6 weeks (± 5 days) for the first 8 assessments (ie, through week 48), and then every 8 weeks (± 5 days) thereafter until withdrawal of consent, disease progression, death, the subject is lost to follow-up, or until the end of study/study termination.

²² EORTC-QLQ-C30, EORTC-QLQ-BIL21, and PGI-S (physical function, appetite loss, and pain) to be conducted pre-dose on C1D1 and cross over C1D1; PGI-C is not collected on C1D1 or cross over C1D1. After EOT visit, the HRQOL will be conducted every 12 weeks until the start of new anticancer therapy.

²³ EQ-5D-5L to be conducted pre-dose on C1D1 and cross over C1D1.

²⁴ For all subjects, plasma samples will be obtained for evaluation of IDH mutations and other genes in circulating tumor DNA at Screening, on C1D15, on Day 1 of every cycle thereafter, and at EOT. No need to repeat on cross over C1D1 if EOT assessment performed within 3 days prior to that date.

²⁵ For all subjects, blood samples must be obtained at Screening, on Day 1 of every cycle thereafter, and at EOT. No need to repeat on cross over C1D1 if EOT assessment performed within 3 days prior to that date.

²⁶ A buccal swab for germ-line mutation analysis will be obtained at Screening.

²⁷ Adverse events will be graded according to the National Cancer Institute Common Terminology Criteria for Adverse Events v4.03. After informed consent has been obtained but prior to initiation of study drug, only serious adverse events (SAEs) caused by a protocol-mandated intervention should be reported. After

initiation of study drug, all AEs and SAEs regardless of attribution will be collected. Any SAEs that are assessed as related to study treatment that occur >28 days post-treatment also are to be reported.

²⁸After a subject discontinues treatment due to progression of disease, they will be contacted every 12 weeks (± 7 days) thereafter for assessment of survival status (OS), HRQOL, and anticancer therapies until death, withdrawal of consent, the subject is lost to follow-up, the occurrence of 150 OS events, or until the end of study/study termination, unless consent to participate is withdrawn.

Table 4: Pharmacokinetic/Pharmacodynamic Sampling (2-HG) and Electrocardiogram Schedule*

Visit/Cycle:	Screening	Cycle 1				Cycle 2		Cycle 3+		EOT ¹		Safety F/U
Study Day:	D -28	D1		D15		D1		D1		D +28		

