10.7. Efficacy Assessments

10.7.1. Response to Treatment

The efficacy of AG-120 will be evaluated by assessing response to treatment according to RECIST v1.1 ([Eisenhauer, et al. 2009](#)) ([Appendix 15.9](#)).

Radiographic assessments (CT or MRI) to obtain tumor measurements are to be conducted at Screening, every 6 weeks for the first 8 assessments (ie, through week 48), and every 8 weeks thereafter (± 5 days) from C1D1, independent of dose-delays and/or dose interruptions, and/or at any time when progression of disease is suspected. CT imaging of the chest, abdomen, and pelvis (Torso) with triphasic IV contrast (30 millisieverts [mSv] per scan) should be performed at baseline and on study. For subjects with allergy to IV iodine contrast, CT of the chest without IV contrast and MRI of the abdomen with IV contrast should be performed at baseline and on study. Brain scans with CT (2 mSv per scan) or MRI should be performed at baseline in subjects with known treated brain metastases and on study at the same imaging time points as Torso imaging. Bone scans (4 mSv per scan) will be performed at baseline if disease is suspected and on study as appropriate as the same imaging time points as Torso imaging. Any ancillary findings on the radiographic assessments will be communicated to the appropriate physician for notification to the subject. The same method (CT or MRI) should be used consistently for any given subject. For subjects randomized to placebo who receive palliative radiotherapy after unblinding and during the cross over period, a repeat CT or MRI will be performed at the end of the 2-week washout period after radiotherapy to document the area that was irradiated and to serve as the new baseline against which all subsequent RECIST v1.1 assessments will be performed, for the purpose of documenting PFS2 during the unblinded open-label cross over period (see [Section 12.12.1](#)). The reading radiologist(s) should be provided the dates and location of the intervening radiation when performing the new baseline assessment. For subjects permitted to continue on open-label AG-120 beyond documented radiographic progression or study unblinding, a new baseline imaging assessment will not be required and the imaging assessments will continue on the current schedule. For subjects who discontinue study drug for reasons other than disease progression, an assessment will be conducted at the EOT Visit and every 6 weeks through week 48, then every 8 weeks thereafter (with the exception of those subjects who initiate a new cancer therapy after discontinuing study treatment) until withdrawal of consent, disease progression, death, the subject is lost to follow-up, or until the end of study/study termination.

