8.1.2. Additional Analyses of PFS

The following analyses of PFS will be performed by treatment arms:

For IRC assessments:

- Stratified log-rank test and Cox regression based on all scans read by IRC prior to crossover, including the scans after local PD from subjects who were originally assigned to AG-120 and continued to stay after unblinding.
- Stratified log-rank test and Cox regression based on PPS set.
- Unstratified log-rank test (one-sided) to compare the two treatment arms. An unstratified Cox regression will be used to estimate the HR (AG-120/placebo) with its 95% CI.
- Subgroup analysis with unstratified log-rank test and unstratified Cox regression model. The HR (AG-120/placebo) with its 95% CI will be displayed for all subgroups graphically in a forest plot. The subgroups will include:
 - The actual number of prior line of therapies in advanced setting (1 vs. ≥ 2)
 - Gender (female vs. male)
 - Extent of disease at screening (locally advanced vs. metastatic)
 - If subject had both local and metastatic, it would be considered as metastatic
 - Intrahepatic vs. extrahepatic
 - Perihilar will be included in extrahepatic category
 - ECOG at baseline (0 vs. ≥ 1)
 - Regions (North America vs. Europe vs. Asia)

In addition, the following exploratory analyses may be performed:

- PFS analysis by excluding subjects who progressed early (≤ 47 days within randomization date, i.e., 6 weeks + 5 days of scan visit window).
- The Cox regression model by including treatment, sum of target lesions at baseline, and other possibly related parameters in covariates.

For Investigator assessments:

- Stratified log-rank test (one-sided) will be utilized to compare the two treatment arms. A stratified Cox regression model will be used to estimate the HR (AG-120/placebo)

with its 95% CI. The same censoring rule as described for the primary PFS based on IRC assessment will be used.

In addition, the concordance of PFS between investigator and IRC assessment will also be summarized by treatment arms and overall.

Table 1: Handling of Missing Response Assessment and Censoring for the Primary Analysis of PFS

Situation	Date of Censoring
No baseline assessment and no death.	Date of the randomization
Alternate anticancer systemic treatment started before documented progression (PD) or death.	Date of last adequate assessment prior to the start of anticancer treatment ¹
No adequate post-baseline assessment and no death.	Date of the randomization

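### The protocol gives conflicting rules on the end-of-treatment scan for subjects who stop to start another anticancer agent, so a progression present at the switch can be censored in primary PFS

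*Protocol*

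**What the plan says.** Five places in the protocol address the EOT tumor assessment.

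- **Section 7.1**, with the same wording in the **Synopsis**, says of subjects who discontinue: "for reasons other than disease progression or start of another anticancer agent, an assessment will be conducted at the EOT Visit". Stopping to start another agent is therefore exempt.
- **Table 3 footnote 20** calls for a response assessment "if the subject discontinues treatment for reasons other than disease progression or start of another anticancer therapy". This is the same exemption.
- **Table 3 footnote 21** has no such exemption: "If a subject goes off treatment for reasons other than disease progression, response assessments will be conducted at the EOT Visit".
- **Section 10.7.1** opens like footnote 21: "For subjects who discontinue study drug for reasons other than disease progression, an assessment will be conducted at the EOT Visit and every 6 weeks". After the 6- and 8-weekly schedule, the same sentence adds a parenthesis: "with the exception of those subjects who initiate a new cancer therapy after discontinuing study treatment".

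Section 7.1 also provides for imaging outside the schedule, "and/or at any time when progression of disease is suspected".

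On the analysis side, Protocol Section 12.7.1 censors at the last response assessment before alternate therapy. SAP Table 1 (Section 8.1.2) gives the censoring date for a subject who starts other systemic therapy before progression or death: "Date of last adequate assessment prior to the start of anticancer treatment". SAP Section 8 drops tumor assessments made after new therapy starts from the response-related summaries.

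**The concern.** Subjects who switch are plausibly not a random subset. Protocol Section 9.13.3 takes a subject off study treatment when the disease requires alternative therapy, so some will be worsening when they stop. For them, a scan before the new agent is the last chance to record a primary PFS event. The censoring rule accepts nothing later.

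If that scan is waived, a progression already present becomes a censored observation dated to the previous scheduled scan. Such censoring is informative. It also varies by site, because the same subject has an EOT scan at a site following footnote 21 and none at a site following Section 7.1. The PFS analyses listed in SAP Section 8.1.2 include none that counts the start of new therapy as an event or disregards it, so the report would not show how far the result depends on this.

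**Working it through.** **1. One subject under each rule.** Take a subject with stable disease at week 12 who stops just before the week 18 scan to start another agent, with no documented progression and no unscheduled scan.

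- Section 7.1, Synopsis, footnote 20: no EOT scan is due. PFS is censored at week 12.
- Footnote 21: an EOT scan is due. If it precedes the new agent and the Independent Radiology Center (IRC) reads progression, this is an event near week 18. If it shows no progression, PFS is censored near week 18.
- Footnote 21, but scanned after the new agent starts: the scan does not count under SAP Table 1, and PFS is censored at week 12. This can happen because the EOT window in Section 7.1 runs to 33 days after last dose.
- Section 10.7.1: either of the first two outcomes, depending on whether the parenthesis covers the EOT scan or only the later scans.

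**2. Age of the censoring scan.** The interval is 6 weeks through week 48 and 8 weeks after that, each ±5 days. One scan 5 days early and the next 5 days late gives at most 42 + 10 = 52 days, or 56 + 10 = 66 days after week 48. A mid-interval switch gives about 3 weeks.

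**3. The plan's own figure.** Protocol Section 12.2 gives HR 0.5, medians of 3 and 6 months, 131 events, 2:1 allocation, one-sided 0.025 and 96% power. Schoenfeld's formula gives |ln 0.5| × √(131 × 2/3 × 1/3) − 1.96 = 0.693 × 5.396 − 1.96 = 1.78, and Φ(1.78) = 96.2%. The stated power is reproduced.

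**4. Chance that a progression lies in the gap.** With exponential PFS, this is 1 − exp(−(ln 2 / median) × gap).

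| Gap | Months (days / 30.4375) | Placebo, median 3 | AG-120, median 6 |
|---|---|---|---|
| 3 weeks | 0.69 | 14.7% | 7.7% |
| 6 weeks | 1.38 | 27.3% | 14.7% |
| 52 days | 1.71 | 32.6% | 17.9% |
| 66 days | 2.17 | 39.4% | 22.2% |

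These are for a subject at the planned average hazard. A subject switched because of worsening disease would have a higher chance.

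**5. Events affected.** The documents give no rate of switching without documented progression. Assume 5-10% of 186 subjects (9-19), equally in both arms, which are planned at 62 placebo and 124 AG-120.

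- 5%, 3 weeks: 0.05 × (62 × 0.147 + 124 × 0.077) = 0.9
- 5%, 6 weeks: 0.05 × (62 × 0.273 + 124 × 0.147) = 1.8
- 10%, 3 weeks: 1.9
- 10%, 6 weeks: 3.5

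That is roughly 1-4 events.

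**The case against.** **Section 10.7.1 does not plainly require the scan.** A reader who stops at its main clause might infer a head-on contradiction with Section 7.1. The parenthesis prevents that reading. It follows the 6- and 8-weekly schedule, and Section 8.5.2 and Table 3 footnote 3 also end follow-up scans at new therapy, so waiving only later scans is the more natural sense. The sentence does not settle it. The one plain opposing text is footnote 21.

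**Table 3 is uncertain evidence.** Footnote 20 refers only to the visit it is attached to, and in the text copy of the table the marks for footnotes 20 and 21 stand in the Safety Follow-up column. That alignment may be unreliable, so nothing rests on it. Footnote 21 names the EOT Visit itself, so its conflict with Section 7.1 and the Synopsis remains on any layout.

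**The scan for suspected progression covers part of the group.** An investigator changing therapy because the disease is worsening will often suspect progression and image. Crossover, which requires documented progression, gives a further reason to do so. This stands and narrows the problem. It does not close it, because the provision depends on the investigator's judgement and the next sentence of Section 7.1 specifically releases these subjects from the EOT scan.

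**Differential censoring would be visible.** Protocol Section 12.7.1 and SAP Section 8.1.1 tabulate censoring reasons by arm. That is correct, but a tabulation does not recover a scan that was never made.

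**Power.** A reader might subtract lost events from 131 and infer lost power, or suppose that every switcher had progressed and count 9-19 lost events. The documents support neither. The cutoff is 131 Investigator-assessed events. A scan never made yields no Investigator event either, so follow-up continues and the main effect is delay. Nothing in the documents gives the share of switchers who have progressed.

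**Conclusion.** The inconsistency is real and stands in current text: the Synopsis, Section 7.1 and footnote 20 exempt these subjects, footnote 21 does not, and Section 10.7.1 is ambiguous. Under the exemption, a switcher with an unscanned progression is censored at a scan that may be 6 weeks old, or 8 weeks after week 48, plus windows. The consequence is informative and site-dependent censoring of the primary endpoint.

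The size is modest: about 15-27% (placebo) and 8-15% (AG-120) per switcher for a 3- to 6-week gap, or roughly 1-4 events in all. This rests on the planned exponential hazards, an assumed 5-10% switching rate equal in both arms, no scan for suspected progression, and an EOT scan that the IRC would have read as progression. The direction of bias depends on which arm switches more and is unknown. No loss of power is claimed. The point merits correction because it touches primary endpoint data and is cheap to fix.

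**What to change.** Reconcile the Synopsis, Section 7.1, Table 3 footnotes 20 and 21 and Section 10.7.1 to one rule: every subject who stops study treatment without documented radiographic progression has the EOT tumor assessment, obtained before any new anticancer agent starts. The timing is essential, because a later scan does not count under SAP Table 1.

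In wording:

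- In the Synopsis, Section 7.1 and footnote 20, delete the part of the exemption that refers to starting another anticancer agent or therapy, leaving progression as the only exempt reason.
- In footnote 21, add that the scan precedes the new agent.
- In Section 10.7.1, state that the parenthesis waives only the later follow-up scans.

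The cost is protocol wording and one scan in a small number of subjects, for whom footnote 21 already requires it. No dose or treatment rule changes, and the SAP censoring rule can stay as it is.

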7.2. Justification of the Study Design

The study is designed as a randomized, double-blind, placebo-controlled efficacy and safety study. Subjects will be randomly assigned in a 2:1 ratio to receive AG-120 or AG-120-matched placebo. Random assignment of subjects avoids bias and helps ensure that both known and

unknown risk factors are distributed evenly between treatment groups. The study includes a matched placebo arm with blinding of all site personnel involved in the evaluation of subjects' response to treatment (eg, Investigators, study coordinators, study pharmacists); this design allows for control of potential influences of the natural course of the disease other than those related to the pharmacologic action of the test drug, and reduces bias in subjective assessments, including both efficacy and safety evaluations. Eligible subjects will continue to receive best supportive care throughout the duration of the study.

An IDMC will review safety data at scheduled intervals as outlined in Section 10.5.1.

Demonstration of the efficacy of AG-120 as assessed by PFS is the primary objective of the study. Response assessments used to determine PFS will be based on standard response criteria (RECIST v1.1) with the primary endpoint based on IRC response assessments.

Secondary endpoints include safety, OS, ORR, DOR, TTR, HRQOL, and health economic outcomes. PFS per Investigator assessment is also a secondary endpoint. Analyses of ORR, DOR, and TTR based on response assessments will be performed as determined by the IRC and by the Investigator.

7.3. Rationale for the Dose Selected

Preliminary data have shown AG-120 to be well tolerated at total daily doses up to 1200 mg in solid tumors (AG120-C-002) and in hematologic malignancies (AG120-C-001); the MTD was not reached in either study. As of a 16 January 2016, 122 subjects have been treated with AG-120 in the AG120-C-002 study, of which 84 subjects received 500 mg QD; 119 subjects have been treated with AG-120 in the AG120-C-001 study, of which 89 subjects received 500 mg QD. Based on a review of the available safety, PK/PD, and clinical activity data observed during dose escalation, 500 mg QD was selected as the AG-120 dose for the expansion phases of both of these trials.

In these studies, there have been minimal dose interruptions, and without an apparent dose relationship for any commonly reported TEAEs or Grade ≥ 3 TEAEs. No DLTs have been reported in Study AG120-C-002. Dose-limiting toxicities of Grade 3 rash and Grade 3 QT prolongation were observed in the 1200 mg QD and 800 mg QD cohorts respectively in Study AG120-C-001; however, expansion of these dose cohorts did not result in identification of the MTD.

Plasma AG-120 exposure increased in a less than proportional manner across doses from 100 mg BID to 1200 mg QD, nearing a plateau at 500 mg QD, in both solid tumors and hematologic malignancies. Sustained and consistent plasma 2-HG inhibition was observed with plasma 2-HG levels reduced to the normal range of healthy volunteers (up to 98.0% inhibition in solid tumors, 99.7% in hematologic malignancies) at all doses, with no apparent dose response. The 500 mg QD dose has shown a maximum PD effect based on 2-HG levels for the majority of subjects.

As of 14 April 2016, AG-120 was associated with clinical activity in subjects with cholangiocarcinoma, including 3 subjects with best overall response of PR and 22 subjects with best overall response of stable disease in the dose escalation and expansion phases of AG120-C-002. Of the 48 subjects with cholangiocarcinoma (both dose escalation and expansion phases) in Study AG120-C-002, 37 subjects received 500 mg QD doses of AG-120.

